## 4 ANALYSIS SETS

In this study 6 analysis populations are defined: Enrolled Set, Exposed Set / Intent to Treat (ITT) Analysis Set, Modified ITT Analysis Set, Per-protocol (PP) set, Safety analysis set (SAF) and Historical control set.

Furthermore, any additional exploratory analysis not identified in the SAP will be identified in the final CSR as exploratory post hoc analyses, including analyses for additional study populations or subgroups of interest.

All disposition and demographic data analysis will be based on the ITT population. All listings will be presented by the ITT population (or Enrolled Set for disposition).

### 4.1 Population Descriptions

The evaluation of participant's inclusion or exclusion to Day 29 analysis population will be done prior data base lock. The evaluation of participant's inclusion or exclusion to Day 181 analysis population will be done prior to final unblinding.

#### 4.1.1 Enrolled Set

All screened participants who provided informed consent, received a participant ID, and were randomized.

#### 4.1.2 Exposed Set / Intent to Treat (ITT) Analysis Set

All participants who received at least one dose of a study vaccine.

The ITT Analysis Set will be analyzed according to the vaccine assigned.

#### 4.1.3 Modified ITT (mITT) Analysis Set

All participants who are randomized, received at least one dose of a study vaccine and provided at least one non-missing post-baseline immunogenicity result. mITT analyses will not be conducted for Day 181.

The mITT will be analyzed according to vaccine assigned.

#### 4.1.4 Per-protocol (PP) set

Participants in the mITT who correctly received all protocol-required doses of study vaccines at Day 1 and who at or prior to the specified timepoint (Day 29 and Day 181) have no evidence of SARS-CoV-2 infection and no protocol deviations impacting the analysis of immunogenicity data. As PP Set for Day 181 is a subset population, these rules are only applicable for the subset. Two PP sets for Day 181 are defined: one is PP (Day 181) and the other one is PP (Day 181) for Cross-Neutralization. Participants in PP (Day 181) need to have Omicron XBB.1.5 results available at Day 181, and participants in PP (Day 181) for Cross-Neutralization need to have cross-neutralization results available at Day 181.

The PP set will be analyzed according to the vaccine assigned.

The following reportable protocol deviations are expected to affect the immunogenicity and will lead to exclusion of a participants from the PPS:

- No informed consent obtained
- Deviations related to dose and administration
- Randomization error/code broken
- Received non-study COVID-19 vaccine
- Received prohibited concomitant medication/other vaccines
- Deviations related to immunogenicity samples up to analysis time point (e.g. no blood sample taken, blood sample taken out of window, blood sample not taken/treated in accordance with lab manual).
- Underlying medical condition forbidden by the protocol or which may influence the immune response

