- Any medically attended AEs (MAAEs), serious AEs (SAEs), AEs of special interest (AESIs), and AEs leading to early study termination and any pregnancies will be reported during the entire study period. This data will be captured by interviewing the participant during the site visits and phone calls and by reviewing available medical records.
- Any medically diagnosed episodes of SARS-CoV-2 infection will be reported as MAAEs; no active surveillance for SARS-CoV-2 infection is planned in this study.

Statistical considerations:

Main analysis population:

Per Protocol Analysis Set (PP)

Includes all participants who received the correctly assigned study vaccines and who have no protocol deviations impacting the analysis of immunogenicity data for the time period summarized as evaluated by the blinded Sponsor Medical Monitor.

Sample Size:

A total sample size of approximately 1680 enrolled participants (1200 participants 18 to 64 years of age, and 480 participants \geq 65 years of age), and a sample size up to 385 participants of study ARCT-154-J01 is proposed for the following study objectives:

1) the coprimary objective 1 of superiority of the ARCT-2303 vaccine (Groups 2a and 2b) compared to a booster dose of ARCT-154 for Omicron XBB.1.5 subvariant

Superiority of $GMT_{ARCT-2303 \text{ (booster)}}$ to $GMT_{ARCT-154 \text{ (booster)}}$

The superiority margin for Omicron XBB.1.5 strain is defined as 1.0 for the GMTs ratio; thus the lower limit of the 2-sided 95% CI for GMT ratios (ARCT-2303/ARCT-154) is higher than 1.0.

Assumptions for the above calculations for the coprimary objective 1) are:

The GMT ratio between the ARCT-2303 (Day 29) and ARCT-154 (booster dose, Day 29) groups is expected to be >1.5 , and the common standard deviation is expected to be 0.60 in the \log_{10} scale.

2) coprimary objective 2 of the noninferiority of the ARCT-2303 vaccine (Groups 2a and 2b) compared to a booster dose of ARCT-154 for the Omicron XBB.1.5 subvariant, in terms of SCR, is also considered:

Noninferiority (NI) of $SCR_{ARCT-2303 \text{ (booster)}}$ versus $SCR_{ARCT-154 \text{ (booster)}}$

CONFIDENTIAL

The noninferiority margin for the Omicron XBB.1.5 subvariant is defined as -5% for the SCRs difference, thus the lower limit of the 2-sided 95% CI for SCR difference (ARCT-2303 minus ARCT-154) is higher than - 5% (i.e., minus 5%).

Assumptions for the above calculations for the coprimary objective 2) are:

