1.2 Schedule of Assessments

The schedule of assessments (SoA) for ARCT-2303-01 is shown in [Table 1](#).

Table 1 Schedule of Assessments

| Visit Type: | Screening and Vacc1 | Follow-up Visit 1 and Vacc2 | Follow-up Visit 2 | Safety call | Final Visit (EOS) | Unscheduled Visit | Early Termination (ET) Visit |
|---|----------------------|-----------------------------|---------------------|-------------|---------------------|------------------------|------------------------------|
| | Clinic ^a | Clinic ^a | Clinic ^a | TC | Clinic ^a | Clinic ^{a, c} | Clinic ^a |
| Study Day: | 1^b | 29 | 57 | 91 | 181 | N/A | N/A |
| Visit Window (days): | -7 | ±3 | ±3 | ±7 | ±7 | N/A | N/A |
| Informed consent | X ^b | | | | | | |
| Weight/height | X ^b | | | | | | |
| Medical history and demographics | X ^b | | | | | | |
| Physical examination ^d | X ^b | X | X | | X | X | X |
| Vital signs, and body temperature ^e | X ^b | X | X | | X | X | X |
| Pregnancy test ^f | X ^b | X | | | | | |
| Testing for COVID-19 ^g | X ^b | X | | | | X ^g | |
| Review of inclusion/exclusion criteria | X ^b | | | | | | |
| Contraindication for second vaccination ^h | | X | | | | | |
| Randomization | X | | | | | | |
| Blood sampling for immunogenicity and safety testing ⁱ | X | X | | | X | (X) | (X) |
| 12-lead electrocardiogram ^j | X | | | | | X | |
| Study vaccine administration ^k | X | X | | | | | |
| Post-vaccination observation ^{e, l} | X | X | | | | | |
| Dispense eDiary and training | X | | | | | | |
| Diary compliance check ^m | X | X | X | | | | |
| Adverse events ⁿ | X ^b | X | X | X | X | X | X |
| Concomitant medication/vaccines collection | X ^b | X | X | X | X | X | X |

Abbreviations: AE, adverse event; AESI, adverse event of special interest; COVID-19, coronavirus disease 2019; ECG, electrocardiogram; eDiary, electronic diary; ET, early termination; MAAE, medically attended adverse event; N/A, not applicable; RT-PCR, real-time polymerase chain reaction; SAE, serious adverse event; SARS-CoV-2, severe acute respiratory syndrome coronavirus 2; TC, telephone call; Vacc, vaccination.

a Visits will be performed in person unless the participant is otherwise directed to be seen at a hospital or to remain at home (if telemedicine/telephone visits are the only feasible option).

CONFIDENTIAL

May not be used, divulged, published or otherwise disclosed without written consent of Arcturus Therapeutics, Inc.

Table 1 Schedule of Assessments

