- g A nasal swab will be collected for validated SARS-CoV-2 rapid antigen testing at Screening to confirm eligibility of participants for recruitment. Prior to each study vaccination, rapid antigen test results must be available for the determination of eligibility. Additional SARS-CoV-2 RT-PCR testing may be performed at planned or unscheduled visits in any participant who is being evaluated for risk of possible COVID-19 infection.
- h For contraindications for the second vaccination and criteria for vaccination delay, refer to Section 5.3.
- i Blood samples will be taken for neutralizing antibody testing before vaccine administration on Days 1 and 29 and on Day 181 for testing of immune responses to SARS-CoV-2 and future exploratory testing, including new emerging SARS-CoV-2 variants. In addition, blood samples may be used for safety testing in case of suspected myocarditis or other potential safety concerns. Blood samples for cardiac enzymes will be collected on Day 1 prior to vaccination (baseline) for all participants. The testing of baseline and post-vaccination samples for cardiac enzymes might be performed based on the investigator's or Sponsor's discretion. In case of early termination from the study due to safety reasons, a blood sample should be collected at the early termination visit. Collection of blood samples at unscheduled visits is at the investigator's discretion for evaluation of safety.
- j A baseline 12-lead ECG at recruitment will be performed on all study participants to identify potential asymptomatic myocarditis and pericarditis cases. In case of suspected myocarditis or pericarditis cases during the study period, detailed evaluation, including ECG, cardiac enzyme testing, and other relevant data should be evaluated. Additional ECG evaluation at unscheduled visits is at the investigator's discretion. Baseline ECG might be performed within 7 days prior to subject recruitment in the study.

CONFIDENTIAL

May not be used, divulged, published or otherwise disclosed without written consent of Arcturus Therapeutics, Inc.

Table 1 Schedule of Assessments

- k Study vaccines will be administered by intramuscular injection into the lateral area of the deltoid muscle of the opposite arms on Day 1. On Day 29, the study vaccine will be administered into the lateral area of the deltoid muscle of a non-dominant arm. Study vaccine will be administered in an observer-blinded fashion.

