As of April 2023, most of the population in developed and low-and middle-income countries received primary vaccination and one booster dose of authorized COVID-19 vaccines. Overall, more than 13.3 billion doses of COVID-19 vaccines were distributed globally, and more than 5.1 billion people are considered fully vaccinated, according to the WHO ([Our World in Data, 2023](#)). In EU/EEA countries, 73.1% of individuals received the primary vaccination series, and 71% received at least one booster dose of COVID-19 vaccines ([European Centre for Disease Prevention and Control, 2023](#)). In the US, 84.6% of individuals completed the primary vaccination series, and 33.1% received a bivalent booster dose of the COVID-19 vaccine ([US CDC, 2023](#)). It is anticipated that, at the time of this study initiation, a significant proportion of the population will receive at least three doses of COVID-19 vaccines. To assess the immunogenicity and safety of ARCT-2303 in a homogeneous population,

CONFIDENTIAL

individuals who received the primary vaccination series and at least one booster dose will be recruited.

The study is active-controlled. At Day 1, all participants will receive 2 vaccine doses in opposite arms (ARCT-2303 and influenza vaccine, ARCT-2303 and placebo, or influenza vaccine and placebo). The assessment of immunogenicity will be performed 28 days after vaccination. To provide equal benefit from the participation in the study and complete seasonal vaccination against COVID-19 and influenza, a switchover vaccine dose (influenza, COVID-19, or placebo) will be administered on Day 29. It allows to keep the blinded design during the entire study period.

Due to the visual differences between the study vaccines, the participants will be blinded before receiving the injection in order to maintain the blinded design of the study. Therefore, the study includes measures to ensure study personnel remains blinded by assigning specific trained and unblinded medical personnel to administer the vaccine. See [Section 6.4](#) for more details.

The duration of immune response after booster vaccination with ARCT-2303 is unknown at the time of study initiation. As such, the kinetics of the immune response after the booster dose and antibody persistence will be assessed at 6 months after vaccination.

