8.5 Rapid COVID-19 Antigen Test

A SARS-CoV-2 Rapid Antigen Test or equivalent will be performed on site prior to each study vaccination to confirm that a participant is eligible for vaccination. A positive test will prevent study vaccination.

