- **Repeat/unscheduled assessments**: Only values collected at scheduled study visits/time points will be presented in summary tables. If a repeat assessment was performed, the result from the original assessment will be presented as the result at the specific visit/time point (early termination visits will not be summarized). All collected data will be included in the data listings.
- **Duplicate entries in eDiary**: For duplicate daily entries in the electronic diary with at least one different value collected between 2 entries, the last data entered will be considered for the analysis (rule established before any planned analysis).
- **Assessment windows**: All assessments will be included in the data listings and no visit windows will be applied to exclude assessments that were performed outside of the protocol specified procedure windows. For safety summaries (where applicable), the table below defines the analysis time windows that correspond to the targeted visit.

Visit (target day)	Visit window (days)
Study Day 1: Screening and Vaccination 1	-7
Study Day 29: Follow-up Visit 1 and Vaccination 2	± 3
Study Day 57: Follow-up Visit 2	± 3
Study Day 91: Safety Call	± 7
Study Day 181: Final Visit (EOS)	± 7

- Result display convention: Results will be center aligned in all summary tables and listings. Participant identifiers visit and parameter labels may be left-aligned if required.
- Date and time display conventions: The following display conventions will be applied in all outputs where dates and/or times are displayed:

Date only: YYYY-MM-DD

Date and time: YYYY-MM-DD HH:MM

If only partial information is available, unknown components of the date or time will be presented as 'NK' (not known), i.e., '2016-NK-NK'. Times will be reported in military time.

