### 8.2 Descriptive Summaries

Results from VNA assay will also be summarized using descriptive statistics for the following parameters:

- Geometric mean titer (GMT) on Days 1, 29 and 181;
- Geometric mean-fold rise (GMFR) as increases of the post-vaccination titer over the pre-vaccination titer;
- Seroconversion rate (SCR) on Day 29 as the percentage of participants in each arm with either:
  - A pre-vaccination titer below the lower limit of quantitation (LLOQ) and a post-vaccination titer  $\geq 4 \times \text{LLOQ}$ ; or
  - A pre-vaccination titer  $\geq \text{LLOQ}$  and a  $\geq 4$ -fold increase in post-vaccination titer.
- Proportion of participants with antibody titer  $\geq \text{LLOQ}$  on Days 1 and 29.

The results of HI and MN will be summarized using descriptive statistics for the following parameters:

- Geometric mean titer (GMT) on Days 1 and 29.
- Geometric mean-fold ratio (GMFR) as increases of the post-vaccination titer over the pre-vaccination titer.
- SCR on Day 29 as the percentage of participants in a group with either:
  - A pre-vaccination titer below the LLOQ for the respective assay and a post-vaccination titer  $\geq 4 \times \text{LLOQ}$ .
  - A pre-vaccination titer  $\geq \text{LLOQ}$  and a  $\geq 4$ -fold increase in post-vaccination titer.
- Proportion of participants with HI titer  $\geq 1:10, 1:20, 1:40, 1:80, 1:160$  and  $1:320$  on Days 1 and 29.

- Proportion of participants with MN titer  $\geq 1:10$ , 1:20, 1:40, 1:80, 1:160 and 1:320 on Days 1 and 29.

There is no formal hypothesis testing for evaluating the co-administration of ARCT-2303 and Fluad Quadrivalent. The results of the analysis will be presented as described above.

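### Scheduled SARS-CoV-2 testing ends at Day 29, so undiagnosed later infections would stay in the Day 181 per-protocol set and push the persistence estimates upward; a sensitivity table should be added

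*SAP*

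**What the plan says.** SAP 4.1.4 uses one infection criterion for both time points: per-protocol participants are those who "at or prior to the specified timepoint (Day 29 and Day 181) have no evidence of SARS-CoV-2 infection".

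How infection is looked for:

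- Protocol 8.5: "A SARS-CoV-2 Rapid Antigen Test or equivalent will be performed on site prior to each study vaccination", which means Day 1 and Day 29.
- Protocol Table 1: the row "Testing for COVID-19" is marked at Day 1, Day 29 and unscheduled visits. It is blank at Days 57, 91 and 181 and at early termination.
- Protocol Table 1, footnote g: "Additional SARS-CoV-2 RT-PCR testing may be performed at planned or unscheduled visits in any participant who is being evaluated" for possible COVID-19. This is optional and depends on suspicion.
- Protocol Synopsis, safety assessments: "no active surveillance for SARS-CoV-2 infection is planned in this study". Diagnosed episodes are recorded as medically attended adverse events.
- Protocol Table 6 has no anti-nucleoprotein assay at any visit. Protocol 2.2 mentions anti-nucleoprotein seronegativity only for the ARCT-154-J01 comparator.

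How the Day 181 result is used: Protocol 2.2.1 says that "the kinetics of the immune response after the booster dose and antibody persistence will be assessed at 6 months after vaccination". Table 6 plans the Day 181 XBB.1.5 assay in subsets of 100 from Group 2a and 100 from Group 2b. SAP 8.2 lists "Geometric mean titer (GMT) on Days 1, 29 and 181" together with GMFR. SAP 4.1.3 rules out a modified ITT analysis at Day 181, and SAP 8.2 describes no sensitivity analysis.

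**The concern.** The set is described in the same words at both time points, but its infection-free status rests on weaker evidence at Day 181. A participant infected after Day 29 and never diagnosed meets the criterion as applied and stays in the set. If the infection raised the XBB.1.5 titer, that rise enters the Day 181 GMT and GMFR and is read as vaccine persistence. The bias has one direction.

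At stake is the trial's evidence on duration of response, which Protocol 2.2.1 says is unknown at study start. No group can serve as an unvaccinated reference at Day 181, because Groups 3a and 3b receive ARCT-2303 on Day 29.

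**Working it through.** The documents give no figure for infection or bias at Day 181, so there is nothing of the plan's own to reproduce. The check has three parts.

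**1. Time after the last scheduled test.** The inputs are the visit days and windows in Protocol Table 1 and SAP 3.1 ("Study Day 29: Follow-up Visit 1 and Vaccination 2", ±3 days; Day 181, ±7 days).

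- Nominal: (181 − 29)/(181 − 1) = 152/180 = 84.4%.
- Lowest within the windows: (174 − 32)/(174 − 1) = 142/173 = 82.1%.
- Highest within the windows: (188 − 26)/(188 − 1) = 162/187 = 86.6%.

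**2. Possible inflation.** Let p be the share of PP (Day 181) with an undiagnosed infection and b the resulting multiple of the Day 181 titer. Both are assumptions. The mean log10 titer rises by p × log10 b, so the GMT is multiplied by b^p. The Day 1 titer is unaffected, so the GMFR is multiplied by the same factor.

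| p | b = 4 | b = 8 |
|---|---|---|
| 10% | 1.15 | 1.23 |
| 20% | 1.32 | 1.52 |

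For scale, the 95% CI factor around a GMT at the planning SD of 0.60 (SAP 13.1) is 10^(t × 0.60/√n). That is 1.32 for n = 100 and 1.21 for n = 200. With p = 20% and b = 4, the shift is as large as the CI half-width in one group of 100. With p = 20% and b = 8, a true 2-fold fall from Day 29 would appear as 2/1.52 = 1.3-fold.

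**3. What a titer-rise cut-off would do.** Take the log10 change from Day 29 to Day 181 as normal with mean −log10 w (w-fold waning) and SD s, independent of the Day 29 titer. The documents give neither w nor s. For cut-off c, let z = (log10 c + log10 w)/s. Among uninfected participants, 1 − Φ(z) are flagged, and removing them multiplies the GMT by 10^(−s × φ(z)/Φ(z)). Example with c = 2, w = 1, s = 0.25: z = 0.301/0.25 = 1.204, flagged 11.4%, factor 0.88.

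No infections at all (flagged, then restricted GMT relative to truth):

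| w | s | 2-fold cut | 4-fold cut |
|---|---|---|---|
| 1 | 0.25 | 11.4%, 0.88 | 0.8%, 0.99 |
| 1.5 | 0.35 | 8.6%, 0.87 | 1.3%, 0.97 |
| 2 | 0.40 | 6.6%, 0.88 | 1.2%, 0.97 |
| 2 | 0.35 | 4.3%, 0.93 | 0.5%, 0.99 |
| 2 | 0.25 | 0.8%, 0.99 | under 0.1%, 1.00 |
| 1 | 0.35 | 19.5%, 0.76 | 4.3%, 0.93 |

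The last row combines no waning with a larger SD and shows that the downward bias can be greater than in the other cases.

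With p = 20% infected and s = 0.25 (GMT inflation, with the share of infected flagged in brackets):

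| w | b | All | 2-fold cut | 4-fold cut |
|---|---|---|---|---|
| 2 | 8 | 1.52 | 1.02 (89%) | 1.20 (50%) |
| 3 | 8 | 1.52 | 1.11 (69%) | 1.34 (24%) |
| 2 | 4 | 1.32 | 1.10 (50%) | 1.26 (11%) |
| 3 | 4 | 1.32 | 1.20 (24%) | 1.30 (3%) |

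The 2-fold cut removes more of the bias but also discards durable responders. The 4-fold cut spares most of them but misses half or more of the infections. Neither is adequate alone.

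**The case against.** **The contrast before and after Day 29 is not clean.** A reader might infer that 16% of the interval is covered and 84% is not. The documents do not support that. Days 1 and 29 are two spot tests, and an antigen test shows only current infection. An infection that clears before Day 29 is also found only by report, so PP (Day 29) has a milder form of the same limit. This stands.

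**Detection after Day 29 is not nil.** Protocol 8.11 provides for interviews and record review, 8.12.5 for a scripted Day 91 call, and 8.12.7 for unscheduled visits with optional RT-PCR. Protocol 5.4 requires COVID-19 treatments to be recorded to study end. These routes reduce the undiagnosed share but do not reach infections that were silent or never tested.

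**The outcome is not shown.** A reader might infer that the Day 181 results will overstate persistence. With no attack rate or post-infection rise in the documents, that remains conditional. Nor is the bias invisible in the planned data: Day 29 and Day 181 titers exist for the same participants and can show rises.

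**A titer rise is not proof of infection.** Protocol 2.2 gives extended antigen expression and durable antibody as potential advantages of a self-amplifying vaccine. A cut-off selects on the outcome and would remove some genuine durable responders. This stands and limits how the analysis may be labelled.

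**The stakes are modest.** The absence of surveillance is openly stated, Day 181 carries no hypothesis test, and SAP 1 allows post hoc analyses. That bears on severity. A prespecified table is still more credible than a post hoc one.

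**Conclusion.** The point holds in conditional form. PP (Day 181) claims no evidence of infection through Day 181, yet no scheduled test covers the last 152 of 180 days (82% to 87% across the visit windows). No planned assay or analysis compensates. If undiagnosed infections occur, the Day 181 XBB.1.5 GMT and GMFR are biased upward. The range of about 1.15 to 1.52 rests wholly on assumed values (10% to 20% infected, 4- to 8-fold boost), so the actual size is unknown.

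The effect is confined to the Day 181 part of secondary objectives 3 and 5. Coprimary objectives 1 to 4 and the Step 3 tests use Day 29, so nothing here touches the success criteria or the ARCT-154-J01 comparison. It is an improvement the sponsor should make, not a defect in the main result.

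**What to change.** Add to SAP 8.2:

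- By group, report the number of PP (Day 181) participants whose XBB.1.5 titer rises at least 2-fold, and at least 4-fold, from Day 29 to Day 181.
- Present the Day 181 GMT and GMFR for all PP (Day 181) participants and, as a sensitivity analysis, without those at or above each cut-off.
- Label these participants *titer rise after Day 29, possible intercurrent infection*; do not call them infected.
- Footnote the Day 181 tables to say that infection after Day 29 was not actively tested for.

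The cost is a paragraph, one repeated table and a footnote. Both titers are already planned for the Day 181 subset, so no new sample or assay is needed.

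The SAP should state the downside. Exclusion depends on the outcome. With no infections, the 2-fold cut lowers the GMT by about 12% to 13% in the first three cases of the no-infection table, and by more if no waning and a large SD coincide. The 4-fold cut costs at most about 3% in those three cases but misses half or more of the infections when waning is 2-fold or greater (for boosts up to 8-fold, SD 0.25). The planned estimate therefore stays, with the restricted ones beside it.
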